### 3.4 Randomization

Patients will be randomized in a 1:1 fashion to either reparixin or placebo.

The randomization list will be generated with a computer procedure by the method of random permuted blocks in which treatment (in blocks of 4) will be balanced within centres. A master randomization list will be generated, randomizing an excess of patients (a maximum of 40 for each site) to allow competitive recruitment within each centre.

The randomization list will be prepared by an independent statistician and provided to Dompé in a sealed envelope to prevent unblinding.

Similarly, individual treatment codes will be provided via a tamper-resistant system (either a sealed envelope or a scratch card). Such a system will definitely allow recognition of whether the code has been broken and guarantees detection of any code misuse. Individual treatment codes will be provided to:

- the Pharmacist (or designee) within each participating site for investigational product preparation;
- the Dompé Pharmacovigilance Department for safety procedures.

The investigators can request to an independent facility (either by telephone or web based system) an individual code in the event of an emergency only, where knowledge of the blinded treatment for that patient could influence further patient care. Any potential unauthorized code break and the reason behind it will be recorded.

The randomization codes will also be accessible to an independent statistician (liaison between the contract research organization [CRO] database and Data Monitoring Committee [DMC] biostatistician) who will generate the reports for the DMC evaluation.

The randomization code will be broken at study completion, i.e. when the last patient has completed his/her last follow-up visit (planned at 365 days after islet infusion), and once the database has been locked.

## 4 STUDY VARIABLES

### 4.1 Primary Variable

The proportion of insulin-independent patients at Day  $365 \pm 14$  days following IAT.

REP0112

Statistical Analysis Plan

For the purpose of this protocol, insulin-independence is defined as freedom from the need to take exogenous insulin for 14 or more consecutive days, with adequate glycemic control, as defined by:

- a glycated hemoglobin (HbA1c) level  $\leq 6.5\%$ ;
- fingerstick fasting blood glucose not exceeding 126 mg/dL more than three times in the past week (based on a minimum of one daily measurement);
- a 2 hour post-prandial blood glucose not exceeding 180 mg/dL more than four times in the past week (based on a minimum of one daily measurement);
- a laboratory fasting glucose in the non-diabetic range ( $<126$  mg/dL).

## 4.2 Secondary Variables

### 4.2.1 Efficacy Variables

- Area under the curve (AUC) for serum C-peptide level during the first 4 hours of a MMTT, normalized by the number of IEQ/kg, at Day 75  $\pm$  14 days and at Day 365  $\pm$  14 days after IAT.
- Average daily insulin requirement at Day 75  $\pm$  14 days and at Day 365  $\pm$  14 days after IAT. For the purpose of this protocol, daily insulin is reported as IU/kg and intake averaged over the previous week.
- Time course of glucose derived from the MMTT at Day 75  $\pm$  14 days and at Day 365  $\pm$  14 days after IAT. For each MMTT, there are 2 basal samples taken separately between -20 to 0 minutes before the meal followed by samples through 240 minutes after the meal.
- Time course of C-peptide derived from the MMTT at Day 75  $\pm$  14 days and at Day 365  $\pm$  14 days after IAT. For each MMTT, there are 2 basal samples taken separately between -20 to 0 minutes before the meal followed by samples through 240 minutes after the meal.
- Time course of insulin derived from the MMTT at Day 75  $\pm$  14 days and at Day 365  $\pm$  14 days after IAT. For each MMTT, there are 2 basal samples taken separately between -20 to 0 minutes before the meal followed by samples through 240 minutes after the meal.
- $\beta$ -cell function as assessed by  $\beta$ -score at Day 75  $\pm$  14 days and at Day 365  $\pm$  14 days after IAT.
- The proportion of patients with HbA1c  $\leq 6.5\%$  at Day 365  $\pm$  14 days after IAT.
- Cumulative number of severe hypoglycemic events from Day 75  $\pm$  14 days to Day 365  $\pm$  14 days after IAT. For the purpose of this protocol, a severe hypoglycemic event is defined as an event with one of the following symptoms: "memory loss, confusion, uncontrollable behavior, irrationale behavior, unusual difficulty in awakening, suspected seizure, seizure, loss of consciousness, or visual symptoms", in which the subject was unable to treat him/herself and which was associated with either a blood glucose level  $<54$  mg/dL or prompt recovery after oral carbohydrate, i.v. glucose, or glucagon administration.
- The proportion of patients with HbA1c  $\leq 6.5\%$  at Day 365  $\pm$  14 days after IAT **AND** free of severe hypoglycemic events from Day 75  $\pm$  14 days to Day 365  $\pm$  14 days after IAT, inclusive.

### 4.2.2 Safety Variables

- Incidence and severity of adverse events (AEs) and serious adverse events (SAEs) throughout the study up to Day 365  $\pm$  14 days after IAT.
- Standard laboratory tests including hematology (hematocrit, hemoglobin, red blood cells, platelets, white blood cells, differential white blood cells count), clinical chemistry (sodium, potassium, serum creatinine, blood urea nitrogen, total bilirubin, ALT, AST), and coagulation

REP0112

Statistical Analysis Plan

(international normalized ratio [INR], partial thromboplastin time [PTT]) at pre-transplant hospital admission and post-transplant hospital discharge.

- Vital signs, i.e. systolic and diastolic blood pressure (BP) and heart rate (HR) at pre-transplant hospital admission and post-transplant hospital discharge.
- ALT, AST, INR, PTT, fibrin degradation products (XDPs), and C-reactive protein (CRP), all daily from Day 1 up to Day 7 after IAT; ALT and AST also on Day 75 ± 5 days after IAT.
- Weight loss from pre-transplant value at Day 75 ± 14 days and Day 365 ± 14 days after IAT.
- Serum level of albumin and pre-albumin, absolute and change from pre-transplant value, at Day 75 ± 14 days and Day 365 ± 14 days after IAT.
- Proportion of patients falling into one of the following levels of steatorrhea severity at Day 75 ± 14 days and Day 365 ± 14 days after IAT.

For the purpose of this protocol, levels of steatorrhea severity (evaluated in the 4 weeks prior to Day 75 ± 14 days and Day 365 ± 14 days), are defined as:

- No steatorrhea;
- Steatorrhea few times per week;
- Steatorrhea daily;
- Stool incontinence.

- Proportion of patients falling into one of the following malnutrition risk levels according to pre-albumin level at Day 75 ± 14 days and Day 365 ± 14 days after IAT.

For the purpose of this protocol, malnutrition risk levels are defined as (adapted from Bernstein, 1995):

- Poor prognosis = pre-albumin level <5.0 mg/dL
- Significant risk = pre-albumin level 5.0 to 10.9 mg/dL
- Increased risk = pre-albumin level 11.0 to 15.0 mg/dL
- Normal = pre-albumin level > 15.0 (up to 35.0) mg/dL

- Cumulative number of episodes of documented hypoglycemia (documented symptomatic; asymptomatic) from Day 75 ± 14 days to Day 365 ± 14 days after IAT.

For the purpose of this protocol, the following definition applies (Diabetes Care, 2005):

- Documented symptomatic hypoglycemia = An event during which typical symptoms of hypoglycemia are accompanied by a measured plasma glucose concentration ≤70 mg/dL.
- Asymptomatic hypoglycemia = An event not accompanied by typical symptoms of hypoglycemia, but with a measured plasma glucose concentration ≤70 mg/dL.

- Cumulative number of diabetic ketoacidosis-related events from Day 75 ± 14 days to Day 365 ± 14 days after IAT.

For the purpose of this protocol, a diabetic ketoacidosis event is defined as the presence of (Pediatrics, 2004):

- Hyperglycemia (blood glucose >200 mg/dL);
- pH <7.3 or HCO3 <15;
- Ketones positive in the serum or urine.

#### 4.2.3 Exploratory Variables

- Time course of inflammatory chemokines/cytokines as assessed by serum level of CXCL8, CCL2 (MCP-1), CCL3, CCL4, CXCL10 (IP-10), CXCL9 (MIG), IL-6, IL-10, INF-γ, TNF-α, and IL-1β at pre-infusion hospital admission (2 basal samples collected 6 to 24 hours apart with both samples obtained before surgery and before investigational product

REP0112

Statistical Analysis Plan

administration is started) and 6, 12, 24, 72, 120, and 168 hours after the end of islet infusion.

- Proportion of patients who are randomized but do not receive IAT.
- Time course of serum microRNA-375 (miR-375) at pre-infusion hospital admission (sample will be obtained before surgery and before investigational product administration is started) and 6, 12, 24, 72, 120, and 168 hours after the end of islet infusion.

#### 4.2.4 Pharmacokinetic Variables

- Plasma levels of reparixin (total and unbound) and relevant metabolites (DF2243Y and ibuprofen) at post-operative Days 1, 3, and 5 (steady state) in all patients; and just prior to, and then at 1, 3, 5, 6, 8, and 12 hours after termination of investigational product administration in a subset of at least 20-24 patients enrolled at Site 1 and Site 3.

Pharmacokinetic summarization and analysis will not be done by the CRO which is conducting summarization and analysis of the primary, secondary, and exploratory variables described in this SAP. Pharmacokinetic summarization and analysis will be described in a separate document and not discussed further in this SAP; pharmacokinetic data collected in the CRF will be listed.

## 5 DEFINITIONS AND DERIVED VARIABLES

Study Day Relative to Date of First Date of Investigational Product Administration: Day 1 will be defined as the first date on which infusion of investigational product is started. Positive study days will be counted forward from Day 1. Day -1 will be the date immediately preceding Day 1, and negative study days will be counted backward from Day -1.

Study Day Relative to Date of Islet Auto-Transplantation: Day 0 will be defined as the date on which islet are infused. Positive study days will be counted forward from Day 0. Day -1 will be the date immediately preceding Day 0, and negative study days will be counted backward from Day -1.

Visit Windows: For the per protocol population (see Section 6 of this SAP), data recorded at the Day 75 and Day 365 visits will be included in summarization and analysis only if the Day 75 and Day 365 visits fall within 14 days of the target study day relative to the date of IAT as indicated in the following table.

Visit	Target Study Day Relative to Date of IAT	Acceptable Range of Study Days Relative to IAT
Day 75	75	61 to 89
Day 365	365	351 to 379

Area Under the Curve (AUC) Normalized by the Number of IEQ/kg, C-peptide: When C-peptide values are below the limit of detection (0.05 ng/mL), a value of 0.05 ng/mL will be assumed in the calculation of area under the curve. Missing C-peptide values will be imputed via linear interpolation, and the average of the two basal samples (values, and mid-point of sample times) will be used as the first sample in the computation of the AUC. Once these rules have been applied to the data, AUC for C-peptide will be computed using the trapezoidal rule, and normalized by dividing the computed AUC value by the total IEQ/kg infused during IAT as recorded on Page 12 of the CRF. For ease of interpretation, the AUC value obtained will be divided by the total time the scale is assessed for reporting purposes. Computation of AUC will be based on actual collection times, unless actual collection time is missing, in which case the scheduled collection time will be used.

REP0112

Statistical Analysis Plan

Other definitions and derived variables are found within the applicable subsections of Section 7, Statistical Methods.

## 6 ANALYSIS POPULATIONS

Five analysis populations will be identified and used in the summarization and analysis of data, namely all screened patients, all randomized patients, intent to treat, per protocol, and safety.

- All Screened Patients: This population will include all patients screened for participation in the trial.
- All Randomized Patients: This population will include all patients randomized to investigational product in the trial.
- Intent to Treat: This population will consist of all patients who are randomized and receive the investigational product (either reparixin or placebo). Summarization and analysis of this population will be based on randomized treatment, regardless of treatment actually received. Eligible patients will be included in this population whether or not they receive IAT, because exclusions cannot be made for events occurring after randomization that could be influenced by the randomized assignment.
- Per Protocol: This population will consist of all patients in the ITT population who meet all of the following criteria:
  - Received IAT
  - Completed 7 days of investigational product dosing
  - No major protocol violations, including violations of inclusion/exclusion criteria, errors in treatment assignment, use of prohibited medication, etc.
  - Visits occurring on Day 75 ± 14 days from IAT and Day 365 ± 14 days from IAT
  - Insulin-independence status recorded at Day 365 ± 14 days from IAT

Further criteria for exclusion from the PP population may be identified during the data review meeting held prior to database lock.

- Safety: This population will consist of all randomized patients. Summarization and analysis of this population will be based on treatment actually received.

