## 9.3. ANALYSIS POPULATION

The Intent to Treat (ITT) population will consist of all patients who are randomized and receive the Investigational Product (either reparixin or placebo); it will be based on the treatment randomized, regardless of the treatment actually received. Patients will be in the ITT analysis whether or not they receive IAT, because exclusions cannot be made for events occurring after randomization that could be influenced by the randomized assignment. The primary and secondary efficacy analyses will be presented primarily for the ITT Population.

The Safety population will consist of all randomized patients and will be based on the treatment actually received. The Safety population will be used to present the demographic and baseline data, and all safety data.

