##### **7.4.1 Patient Disposition**

The number of patients screened in total will be presented. The number of patients randomized and number and percentage of randomized patients who did not receive IAT, who were treated, who were included and treated/included and not treated/excluded from the safety population (with reason for exclusion [not randomized] presented as a percentage of patients screened in total only), who were included/excluded from the ITT population (with reason for exclusion), who were included/excluded from the PP population (with reason for exclusion), who completed the study, and who withdrew early from the study (with primary reason for early withdrawal) will be presented by treatment group and in total. The number and percentage of randomized patients who were included in the safety population will be summarized by treatment as received, or by treatment as randomized for those not treated. Fisher's exact test will be used to compare between treatment groups the proportion of randomized patients who did not receive IAT.

Screening data recorded for patients who do not proceed to transplant with study drug administration will be listed separately.

Patient disposition at each site will be presented by treatment group and in total, with the exception of there being no comparison between treatment groups of the proportion of randomized patients who did not receive IAT.

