### 7.6.1 Adverse Events

All reported verbatim adverse event terms will be mapped to standard system organ classes and preferred terms using the MedDRA Dictionary as specified in the Data Management Plan for this protocol.

REP0112

Statistical Analysis Plan

A treatment emergent adverse event (TEAE) is defined as any recorded adverse event which started on or after Day 1 of investigational product administration. If the start date of an adverse event is incomplete or missing, the event will be assumed to be a TEAE, unless the incomplete start date (month and/or year) or the stop date (complete or incomplete) clearly indicates that the event started prior to dosing.

The relationship of each adverse event to investigational product will be recorded as none, unlikely, possible, probable, or highly probable. If a relation is missing for an adverse event, the relation of the event to investigational product will conservatively be assumed to be highly probable for summarization.

The severity of each adverse event will be classified as mild, moderate, or severe. If the severity of an adverse event is missing, the severity of the event will conservatively be assumed to be severe for summarization.

Serious adverse events will be those events indicated as such on the CRF (a "Yes" response to "Serious").

An overview of TEAEs will summarize the number and percentage of patients and the number of events in the following categories: any TEAE, any TEAE by relationship to investigational product, any TEAE by severity, any serious TEAE, any serious TEAE by relationship to investigational product, any serious TEAE by severity, any TEAE resulting in early withdrawal from study, and death. For this overview, patients and events will be counted at each level of relationship to investigational product or severity at which an event is experienced (and not by worst relationship to investigational product and maximum severity).

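### The Safety population includes never-dosed patients, so treatment-emergent event rates are understated in the total column if anyone is undosed, and the column for such patients is unsettled

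*SAP*

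**What the plan says.** Protocol and SAP agree on the definition. Protocol 9.3 states: "The Safety population will consist of all randomized patients and will be based on the treatment actually received". SAP section 6 repeats it: "This population will consist of all randomized patients. Summarization and analysis of this population will be based on treatment actually received". Neither requires dosing. The ITT population in SAP section 6 does: "This population will consist of all patients who are randomized and receive the investigational product (either reparixin or placebo".

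That undosed patients are meant to be in the Safety population is clear from SAP 7.4.1. The disposition table is to count randomized patients "who were included and treated/included and not treated/excluded from the safety population", and the only reason it gives for exclusion is not having been randomized.

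SAP 7.6 uses this population for all safety data, and SAP 7.6.1 tabulates TEAEs by treatment group and in total. A TEAE is "any recorded adverse event which started on or after Day 1 of investigational product administration", and SAP section 5 sets Day 1 as the date on which infusion starts.

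Three sections bear on the column in which an undosed patient appears:

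- SAP 6 goes by treatment actually received.
- SAP 7.4.1 counts Safety patients by treatment received, "or by treatment as randomized for those not treated".
- SAP 7.4.7 shows patients who received no product in the total column only.

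**The concern.** An undosed patient can be in the denominator of a TEAE percentage but, except through the missing-date default, cannot be in the numerator. A table of treatment-emergent harm then reads lower than the rate among people exposed to the infusion. That is the wrong direction of error for a safety table.

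The usual roles of the populations are also exchanged. The ITT set requires dosing and the Safety set does not. As defined, the Safety set has the same members as the All Randomized set, and no population consists of dosed patients analysed by the product they received.

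A separate problem does not depend on size. Treatment actually received is undefined for an undosed patient, and the SAP gives no rule for the TEAE tables, so two programmers could defensibly produce different arm denominators. SAP section 8 has the independent statistician use this SAP as a guideline for the monitoring committee's outputs, so the ambiguity could carry into the ongoing safety review.

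**Working it through.** The plan states neither a number of undosed patients nor a TEAE rate, so there is no figure of its own to reproduce. The check has two parts.

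**1. Does the text produce the dilution?**

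- A patient can be randomized and never dosed: Protocol 7.1.1 places randomization before the start of infusion.
- That patient is in the Safety population (SAP 6, 7.4.1; Protocol 9.3).
- With no infusion there is no Day 1 (SAP 5), so no dated event can start on or after it (SAP 7.6.1).
- SAP 7.1 takes percentages over non-missing responses in the analysis population and treatment group unless otherwise stated. Nothing in SAP 7.6.1 states otherwise or limits the denominator to dosed patients.
- Exception: SAP 7.6.1 treats an event with an incomplete or missing start date as a TEAE unless the available dates show onset before dosing. Undosed patients are not excluded from that default.

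**2. How large is it?**

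Reported rate = true rate among dosed patients × dosed / (dosed + undosed).

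Inputs from the documents:

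- About 100 patients with islet auto-transplantation (IAT) and about 5 others without it, 105 in all (Protocol 9.1, SAP 3.3).
- At the time of the protocol amendment, 86 of 89 randomized patients had received the procedure, so 3 had not.

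Assumptions: 1 to 5 of 105 undosed, or 3 of 89, and a true TEAE rate of 50% for illustration. Not receiving IAT is not the same as being undosed, so 5 is the top of the assumed range and not an estimate.

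Total column:

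| Undosed / randomized | Factor | A true 50% reads |
|---|---|---|
| 0 / 105 | 105/105 = 1.000 | 50.0% |
| 1 / 105 | 104/105 = 0.990 | 49.5% |
| 3 / 105 | 102/105 = 0.971 | 48.6% |
| 5 / 105 | 100/105 = 0.952 | 47.6% |
| 3 / 89 | 86/89 = 0.966 | 48.3% |

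For 1 to 5 undosed of 105, the relative understatement is 1.0% to 4.8%.

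Arm column, with 50 dosed patients in the arm:

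| Placement of undosed patients | Factor | A true 50% reads |
|---|---|---|
| Total column only (SAP 7.4.7) | 1.000 | 50.0% |
| As randomized (SAP 7.4.1), 2 in the arm | 50/52 = 0.962 | 48.1% |
| As randomized, 3 in the arm | 50/53 = 0.943 | 47.2% |
| As randomized, all 5 in one arm | 50/55 = 0.909 | 45.5% |

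If 5 undosed patients split 3 and 2, two arms with the same true 50% would read 47.2% and 48.1%, a spurious gap of 0.9 percentage points. The extreme of 5 and 0 gives 45.5% against 50.0%, a gap of 4.5 points.

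**The case against.** The strongest reply is that the consequence is narrow and probably small. Most of that stands.

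- **Arm columns.** A reader might infer that the SAP puts undosed patients into the TEAE denominators of their randomized arm. The documents do not support this as a stated rule. The sentence in SAP 7.4.1 governs how the disposition table counts Safety patients. SAP 6 goes by treatment received, which an undosed patient lacks, and SAP 7.4.7 uses the total column only. On that last reading the between-arm comparison is not diluted.
- **Other safety tables.** A reader might also infer that every laboratory and exposure percentage is biased. It is not. Laboratory percentages use non-missing results at each visit, so an undosed patient without a discharge sample does not enter the discharge denominator, and screening results precede dosing in any case. SAP 7.4.7 reports undosed patients openly, and amounts infused are continuous summaries. Exploratory summaries use observed samples.
- **Number undosed.** Patients without IAT may well have been dosed. Infusion starts 6 to 18 hours before islet infusion (Protocol 6.2), and Protocol 6.3.2 provides for stopping the product when the transplant does not take place. The 3 of 89 may include dosed patients. Placing 3 to 5 undosed patients in one arm is a worst case. Blinding and blocked 1:1 randomization within centres make a marked imbalance unlikely.
- **Transparency.** The tables give numbers of patients with events, the disposition table counts the untreated, and screening data for patients who do not go on to transplant with study drug are listed separately. A reader could recompute the total-column rates.

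These points limit size and reach. They leave a denominator that admits patients who are not at risk of the event as defined, and no rule saying which column they belong in. The non-missing rule in SAP 7.1 does not remove them from TEAE tables, because the SAP nowhere says that an undosed patient's TEAE status is missing.

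**Conclusion.** The point holds for TEAE incidence. In the total column, understatement follows directly from the definitions whenever at least one randomized patient is undosed. In the arm columns it follows only if undosed patients are counted as randomized, which the SAP leaves open.

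On the assumed range of 1 to 5 undosed of 105, total-column rates are 1.0% to 4.8% too low in relative terms. If nobody is undosed there is no effect on the rates, though the definition and the placement rule would still be unclear.

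Laboratory, exposure-amount and exploratory summaries are largely unaffected. The primary analysis, the power calculation and the committee's guidelines on unexpected deaths do not use this population. Protocol and SAP agree on the definition, so this is an analysis choice to correct and not a discrepancy between the documents. The likely size is modest, but the correction is cheap and should be made before database lock.

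**What to change.** In SAP section 6, define the Safety population as randomized patients who received any amount of investigational product, analysed by the product received. If the sponsor prefers to keep the present population, state at least that TEAE denominators, by arm and in total, are limited to dosed patients.

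Consequential edits:

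- Align SAP 7.4.1 and 7.4.7 with SAP 6 so that undosed patients are handled one way throughout. The All Randomized population already serves for counting them.
- Limit the missing-start-date default in SAP 7.6.1 to dosed patients.
- List undosed patients, and any adverse events recorded for them, separately.
- Record the departure from Protocol 9.3 in SAP 1.2, or amend Protocol 9.3 to match.

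The cost is one definition and a few aligned sentences. No new data are needed.
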